8.2 Populations for Analyses

The first (primary) analysis will be carried out for the primary endpoint and safety- and PK-related secondary endpoints when all subjects who are still on-treatment have completed the Part 1 period. The final analysis will be carried out for the efficacy-related secondary endpoints and, if data are available, the exploratory endpoints when all subjects have had at least 9 months of follow-up.

Since the primary objective will be addressed by a safety endpoint, the primary endpoint analysis will be based on all treated subjects. For consistency, the secondary endpoints will use the same analysis population as the primary endpoint (ie, all treated subjects).

- All Enrolled Subjects: All subjects who signed an informed consent form and were registered into the IRT.
- All Randomized Subjects: All subjects who were randomized to any treatment group. This is the primary dataset for efficacy listings.
- All Treated Subjects: All subjects who received at least one dose of any study medication. This is the primary dataset for analysis of study conduct, study population, efficacy (including secondary endpoints), exposure, and safety (including primary endpoint).
- PK Subjects: All treated subjects with available serum time-concentration data.
- Immunogenicity Subjects: All treated subjects with available ADA data.
- Biomarker Subjects: All treated subjects with available biomarker data.

8.3 Endpoints

8.3.1 Primary Endpoint(s)

The primary endpoint of the study is the incidence of AEs in the Broad Scope MedDRA Anaphylactic Reaction SMQ occurring within 2 days after dosing during the combination, Part 1 period. This incidence rate is defined as number of subjects who experienced at least 1 AE in the MedDRA Anaphylactic Reaction broad scope SMQ with onset on the day of or within 2 days after any study therapy infusion during the combination period (Part 1) divided by number of treated

subjects. For reference, the terms currently included in the MedDRA Anaphylactic Reaction SMQ based on MedDRA version 19.0 are listed in [Table 8.3.1-1](#).

The analysis of the primary endpoint will occur at the time of first (primary) analysis when all subjects who are still on-treatment have completed the Part 1 period.

Table 8.3.1-1: Preferred Terms Included in the MedDRA Anaphylactic Reaction SMQ - Broad and Narrow Scopes

Preferred Term ^a	Term Scope ^b
Acute respiratory failure	Broad
Allergic oedema	Broad
Anaphylactic reaction	Narrow
Anaphylactic shock	Narrow
Anaphylactic transfusion reaction	Narrow
Anaphylactoid reaction	Narrow
Anaphylactoid shock	Narrow
Angioedema	Broad
Asthma	Broad
Blood pressure decreased	Broad
Blood pressure diastolic decreased	Broad
Blood pressure systolic decreased	Broad
Bronchial oedema	Broad
Bronchospasm	Broad
Cardiac arrest	Broad
Cardio-respiratory arrest	Broad
Cardio-respiratory distress	Broad
Cardiovascular insufficiency	Broad
Chest discomfort	Broad
Choking	Broad
Choking sensation	Broad
Circulatory collapse	Narrow
Circumoral oedema	Broad
Cough	Broad
Cyanosis	Broad
Dialysis membrane reaction	Narrow
Diastolic hypotension	Broad
Dyspnoea	Broad
Erythema	Broad
Eye oedema	Broad
Eye pruritus	Broad
Eye swelling	Broad
Eyelid oedema	Broad
Face oedema	Broad
Flushing	Broad

Table 8.3.1-1: Preferred Terms Included in the MedDRA Anaphylactic Reaction SMQ - Broad and Narrow Scopes

Preferred Term ^a	Term Scope ^b
Generalised erythema	Broad
Hyperventilation	Broad
Hypotension	Broad
Injection site urticaria	Broad
Irregular breathing	Broad
Kounis syndrome	Narrow
Laryngeal dyspnoea	Broad
Laryngeal oedema	Broad
Laryngospasm	Broad
Laryngotracheal oedema	Broad
Lip oedema	Broad
Lip swelling	Broad
Mouth swelling	Broad
Nasal obstruction	Broad
Nodular rash	Broad
Ocular hyperaemia	Broad
Oedema	Broad
Oedema mouth	Broad
Oropharyngeal spasm	Broad
Oropharyngeal swelling	Broad
Periorbital oedema	Broad
Pruritus	Broad
Pruritus allergic	Broad
Pruritus generalised	Broad
Rash	Broad
Rash erythematous	Broad
Rash generalised	Broad
Rash pruritic	Broad
Respiratory arrest	Broad
Respiratory distress	Broad
Respiratory failure	Broad
Reversible airways obstruction	Broad
Sensation of foreign body	Broad
Shock	Narrow
Shock symptom	Narrow

Table 8.3.1-1: Preferred Terms Included in the MedDRA Anaphylactic Reaction SMQ - Broad and Narrow Scopes

Preferred Term ^a	Term Scope ^b
Skin swelling	Broad
Sneezing	Broad
Stridor	Broad
Swelling	Broad
Swelling face	Broad
Swollen tongue	Broad
Tachypnoea	Broad
Throat tightness	Broad
Tongue oedema	Broad
Tracheal obstruction	Broad
Tracheal oedema	Broad
Type I hypersensitivity	Narrow
Upper airway obstruction	Broad
Urticaria	Broad
Urticaria papular	Broad
Wheezing	Broad

^a Changes may be made to this list with each new version of MedDRA. For information, the preferred terms defined at the time of finalization of this document are listed using MedDRA version 19.0.

^b All Narrow Scope PTs are also included in the Broad Scope.

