4.5.6 Treatment of Related Infusion Reactions

Since study drug contains only human immunoglobulin protein sequences, it is unlikely to be immunogenic and induce infusion or hypersensitivity reactions. However, if such a reaction were to occur, it might manifest with fever, chills, rigors, headache, rash, pruritus, arthralgias, hypotension, hypertension, bronchospasm, or other allergic-like reactions. All Grade 3 or 4 infusion reactions should be reported within 24 hours to the study medical monitor and reported as an SAE if it meets the criteria. Infusion reactions should be graded according to NCI CTCAE (Version 4.0) guidelines.

Treatment recommendations are provided below and may be modified based on local treatment standards and guidelines, as appropriate:

For Grade 1 symptoms: (mild reaction; infusion interruption not indicated; intervention not indicated):

- Remain at bedside and monitor subject until recovery from symptoms. The following prophylactic premedications are recommended for future infusions: diphenhydramine 50 mg (or equivalent) and/or acetaminophen/paracetamol 325 to 1000 mg at least 30 minutes before additional nivolumab administrations

For Grade 2 symptoms: (moderate reaction required therapy or infusion interruption but responds promptly to symptomatic treatment (eg, antihistamines, non-steroidal anti-inflammatory drugs, narcotics, corticosteroids, bronchodilators, IV fluids); prophylactic medications indicated for ≤ 24 hours):

- Stop the study drug infusion, begin an IV infusion of normal saline, and treat the subject with diphenhydramine 50 mg IV (or equivalent) and/or acetaminophen/paracetamol 325 to 1000 mg; remain at bedside and monitor subject until resolution of symptoms. Corticosteroid and/or bronchodilator therapy may also be administered as appropriate. If the infusion is interrupted, then restart the infusion at 50% of the original infusion rate when symptoms resolve; if no further complications ensue after 30 minutes, the rate may be increased to 100% of the original infusion rate. Monitor subject closely. If symptoms recur, then no further study drug will be administered at that visit
- For future infusions, the following prophylactic premedications are recommended: diphenhydramine 50 mg (or equivalent) and/or acetaminophen/paracetamol 325 to 1000 mg should be administered at least 30 minutes before nivolumab infusions. If necessary, corticosteroids (up to 25 mg of hydrocortisone or equivalent) may be used

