8 STATISTICAL CONSIDERATIONS

8.1 Sample Size Determination

Approximately 102 subjects will be randomized to the 2 treatment arms in a 1:1 ratio in order to target 100 treated subjects (50 per arm). This number of treated subjects was chosen to achieve a sufficient level of precision for a descriptive analysis to estimate the difference in rates of AEs in the Broad Scope MedDRA Anaphylactic Reaction SMQ between the two treatment arms. Fifty treated subjects per arm will allow estimation of the rate difference within 95% confidence limits of +/- 20% or less and will be supplemented by a qualitative clinical assessment of the type and severity of events to evaluate benefit-risk.

In previously submitted Phase 2/3 studies of nivolumab in combination with ipilimumab (CA209069 and CA209067), AEs in the MedDRA Anaphylactic Reaction SMQ (broad scope) with onset within 2 days after sequential dosing of nivolumab 1 mg/kg combined with ipilimumab 3 mg/kg were reported in 24% of treated subjects. In the current study, if the observed rate of these events is equal to 24% among 50 treated subjects in each arm, then the 95% CI for the difference in rates between arms will be (-16.7%, 16.7%).

Table 8.1-1 shows the precision that the sample size of 50 treated subjects per arm will provide for estimating rates and rate differences between the treatment arms under different assumed observed rates.

Table 8.1-1: 95% CI for Rates and Rate Differences when Observed in 50 Subjects per Arm

Observed AE Rate (95% CI)		Observed Rate Difference (95% CI)
Arm A (Co-administration, FRC)	Arm B (Sequential administration)	Arm A - Arm B
24% (13.1%, 38.2%)	22% (11.5%, 36.0%)	2% (-14.5%, 18.5%)
24% (13.1%, 38.2%)	24% (13.1%, 38.2%)	0% (-16.7%, 16.7%)
26% (14.6%, 40.3%)	24% (13.1%, 38.2%)	2% (-15.0%, 19.0%)
30% (17.9%, 44.6%)	28% (16.2%, 42.5%)	2% (-15.8%, 19.8%)
30% (17.9%, 44.6%)	30% (17.9%, 44.6%)	0% (-18.0%, 18.0%)

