8.3.2 Secondary Endpoint(s)

The first secondary endpoint is the incidence of AEs in the MedDRA Anaphylactic Reaction narrow scope SMQ occurring within 2 days after any study therapy infusion during the combination period (Part 1). This incidence rate will be defined similarly to the primary endpoint except that the event rate will be based on terms within the narrow scope SMQ rather than the broad scope.

The second secondary endpoint is the incidence of events within the hypersensitivity/infusion reaction select AE category occurring within 2 days after any study therapy infusion during the combination period (Part 1). The select AEs consist of a list of preferred terms defined by the Sponsor and represent AEs with a potential immune-mediated etiology. At the time of this writing the following 5 MedDRA preferred terms are included in the hypersensitivity/infusion reaction select AE category: Anaphylactic Reaction, Anaphylactic Shock, Bronchospasm, Hypersensitivity, and Infusion Related Reaction. Changes may be made to this list with each new version of MedDRA prior to database lock. The list that is the most current at the time of analysis will be used. The incidence rate of hypersensitivity/infusion reaction select AEs will be defined

similarly to the primary endpoint except that the event rate will be based on terms from the hypersensitivity/infusion reaction select AE category rather than the MedDRA Anaphylactic Reaction broad scope SMQ.

The third secondary endpoint is the drug-related Grade 3 - 5 AE incidence rate defined using NCI CTCAE version 4.0 criteria. The drug-related Grade 3 - 5 AE rate is defined as number of subjects who experienced at least 1 AE of Grade 3 or higher, judged to be related to study drug by the investigator, and with onset on or after the first dose of study treatment and within 30 days of the last dose of study treatment, divided by number of treated subjects.

The fourth secondary endpoint is the all causality Grade 3 - 5 AE incidence rate defined using NCI CTCAE version 4.0 criteria. The all causality Grade 3 - 5 AE rate is defined as number of subjects who experienced at least 1 AE of Grade 3 or higher with onset on or after the first dose of study treatment and within 30 days of the last dose of study treatment, divided by number of treated subjects.

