## 4 ENDPOINTS

### 4.1 Primary Endpoint: MedDRA Anaphylactic Reaction Broad Scope SMQ AE Incidence Rate

The primary endpoint of the study is the incidence of AEs in the Broad Scope MedDRA Anaphylactic Reaction SMQ occurring within 2 days after dosing during the combination, Part 1 period. This incidence rate is defined as number of subjects who experienced at least 1 AE in the MedDRA Anaphylactic Reaction broad scope SMQ with onset on the day of or within 2 days after any study therapy infusion during the combination period (Part 1) divided by number of treated subjects. For reference, the terms currently included in the MedDRA Anaphylactic Reaction SMQ based on MedDRA version 19.0 are listed in [Table 4.1-1](#).

The analysis of the primary endpoint will occur when all treated subjects who are still on-treatment complete the Part 1 period.

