## 7 STATISTICAL ANALYSES

### 7.1 General Methods

Unless otherwise noted, the following subsections describe tabulations of discrete variables, by the frequency and proportion of subjects falling into each category, grouped by treatment (with total). Percentages given in these tables will be rounded and, therefore, may not always sum to 100%. Continuous variables will be summarized by treatment group (with total) using the mean, standard deviation, median, minimum and maximum values. If a missing category is not being presented in the data display, only those subjects with non-missing values for the parameter being assessed are included in the percentage calculation.

Time to event distribution will be estimated using Kaplan Meier techniques. This will be done for endpoints progression free survival, overall survival and duration of response (note that TTR will be analyzed using summary statistics such as mean, SD, median, min, max). Median survival time along with 95% CI will be constructed based on a log-log transformed CI for the survivor function  $S(t)$ . Rates at fixed time points will be derived from the Kaplan Meier estimate and corresponding confidence interval will be derived based on Greenwood formula for variance derivation and on log-log transformation applied on the survivor function  $S(t)$ .

Confidence intervals for binomial proportions will be derived using the Clopper-Pearson method.

Formal hypothesis testing with control of Type I error will not be conducted for any of the endpoints in this study. No p-values will be presented. Confidence intervals, when presented, will be for descriptive purposes only and will not be adjusted for multiplicity.

Unless otherwise noted, safety analyses will be performed using the on-treatment definition for the entire study treatment period (i.e. combined Part 1 and Part 2 treatment periods) as defined in Section 6.1.2. Alternate analysis periods will be used for specific endpoints or selected analyses as described in the corresponding endpoint or analysis section of this SAP.

Please see the following sections for additional details:

- Section 4.1: Primary Endpoint: MedDRA Anaphylactic Reaction Broad Scope SMQ AE Incidence Rate
- Section 4.2.1: MedDRA Anaphylactic Reaction Narrow Scope SMQ AE Incidence Rate

- Section 4.2.2: Hypersensitivity/Infusion Reaction Select AE Incidence Rate
- Section 4.2.6: Objective Response Rate

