## **7.6 Safety**

### **7.6.1 MedDRA Anaphylactic Reaction Broad Scope SMQ AE Incidence Rate**

For purposes of the primary endpoint analysis, the incidence rate of AEs in the Broad Scope MedDRA Anaphylactic Reaction SMQ occurring within 2 days after any dose in the Part 1 dosing period will be reported by treatment arm for all treated subjects. Corresponding 95% CIs for the rate in each treatment arm will be calculated using the Clopper-Pearson method. An estimate and confidence interval for the difference in rates between treatment arms will be presented based on CMH method of weighting, adjusting for PD-L1 status and M Stage at screening.

Additional characterization of the events meeting the primary endpoint criteria will be provided, including summaries by system organ class (SOC) and preferred term (PT). Adverse events will be coded using the Medical Dictionary for Regulatory Activities (MedDRA), and the most recent version of the dictionary at the time of the database lock will be used. Adverse events results will be graded for severity using NCI Common Terminology Criteria for Adverse Events (CTCAE) Version 4.0 criteria. In the AE summary tables subjects will be counted by worst CTC grade only once at the Preferred Term (PT), only once at the System Organ Class (SOC), and only once at subject level for the counting of total number of subjects with an AE. The AE tables will list the SOCs (ordered by descending frequency) and the PTs (ordered by descending frequency within each SOC) for each treatment group.

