### **7.6.3 Hypersensitivity/Infusion Reaction Select AE Incidence Rate**

The incidence rate of hypersensitivity/infusion reaction select AEs by treatment arm, the difference in rates between arms, and the corresponding 95% confidence intervals will be reported using the

same methods as described above for the primary endpoint analysis. Summaries by worst CTC grade, SOC, and PT will also be provided similar to the primary endpoint.

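### Does the primary analysis need a combined rate because the broad-scope SMQ leaves out 'Infusion related reaction' and 'Hypersensitivity'?

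*Protocol*

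**What the plan says.** **Primary endpoint.** A subject counts for "at least 1 AE in the MedDRA Anaphylactic Reaction broad scope SMQ with onset on the day of or within 2 days after" any Part 1 infusion, over treated subjects (Protocol 8.3.1; SAP 4.1). The SAP presents its table as a reference list: "the terms currently included in the MedDRA Anaphylactic Reaction SMQ based on MedDRA version 19.0 are listed in" Table 4.1-1. SAP 7.6.1 codes events with the dictionary version current at database lock. For the comparison it states: "An estimate and confidence interval for the difference in rates between treatment arms will be presented based on CMH method of weighting", adjusted for PD-L1 status and M stage.

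**Second secondary endpoint.** Protocol 8.3.2 names five select-AE terms: "Anaphylactic Reaction, Anaphylactic Shock, Bronchospasm, Hypersensitivity, and Infusion Related Reaction". The window and denominator are those of the primary endpoint, but this list replaces the SMQ list. SAP 7.6.3 reports "The incidence rate of hypersensitivity/infusion reaction select AEs by treatment arm, the difference in rates between arms, and the corresponding 95% confidence intervals" by the primary-endpoint methods, and adds summaries by worst grade, system organ class and preferred term.

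**Clinical description.** Of an infusion or hypersensitivity reaction, Protocol 4.5.6 says "it might manifest with fever, chills, rigors, headache, rash, pruritus, arthralgias, hypotension, hypertension, bronchospasm, or other allergic-like reactions".

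**Inference.** SAP 7.1: "Formal hypothesis testing with control of Type I error will not be conducted for any of the endpoints in this study". Protocol 8.1 adds a qualitative clinical review of what kinds of events occurred and how severe they were.

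**The concern.** The trial compares one fixed-ratio infusion with two sequential infusions, so a reaction that a site records as an infusion reaction is directly relevant. Yet a subject whose only coded event is *Infusion related reaction* or *Hypersensitivity* is a non-event on the primary endpoint, whatever the grade. The study is open-label. If one arm's sites tend to write down the diagnosis and the other's the symptoms, the primary difference could move for reasons unrelated to the drug.

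The secondary endpoint does not fully answer this. The two lists share three terms and one subject can appear in both, so the two rates cannot be added. A reader given only the two headline rates cannot tell how many subjects per arm had either kind of event. What is at stake is how clearly a descriptive comparison can be read. No error rate is involved.

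**Working it through.** **1. The plan's own precision figure.** Inputs from Protocol 8.1: 50 treated subjects per arm, and earlier broad-scope events that "were reported in 24% of treated subjects". The unstratified Wald half-width is

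1.96 × √(2 × 0.24 × 0.76 / 50) = 1.96 × 0.0854 = 0.167.

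This matches the stated (-16.7%, 16.7%). All five rows of Table 8.1-1 reproduce to 0.1 point in the same way, with Clopper-Pearson limits for the single-arm rates.

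**2. Term match.** The primary list has 86 terms; narrow-scope terms are included in the broad scope.

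| Select-AE term | In the primary list? |
|---|---|
| Anaphylactic reaction | Yes |
| Anaphylactic shock | Yes |
| Bronchospasm | Yes |
| Hypersensitivity | No (only *Type I hypersensitivity* is listed) |
| Infusion related reaction | No |

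Of the ten signs named in Protocol 4.5.6, four are listed (rash, pruritus, hypotension, bronchospasm) and six are not (fever, chills, rigors, headache, arthralgias, hypertension). That section's list is open-ended, and the table holds many other allergic-type signs, such as urticaria, flushing, angioedema, wheezing and dyspnoea.

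**3. Size.** Protocol 4.3.1 gives 3.2% hypersensitivity/infusion reactions for the combination in one earlier study, without a term list or window. Assume it applies here:

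- Subjects in the whole category: 0.032 × 50 = 1.6 per arm.
- Combined rate: from 24.0% (all already primary events) to 24.0 + 3.2 = 27.2% (none already counted).
- Half-width at 27.2%: 1.96 × √(2 × 0.272 × 0.728 / 50) = 17.4 points, against 16.7 at 24%.
- Largest unstratified half-width, at 50%: 1.96 × √(2 × 0.5 × 0.5 / 50) = 19.6 points, within the stated 20. The planned interval is stratified, so this is a guide.

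**4. What the planned outputs leave open.** Take 12/50 primary and 2/50 select-AE subjects in each arm. Both planned differences are 0. The combined count is 12 to 14 per arm, so its difference lies between (12 - 14)/50 = -4 and (14 - 12)/50 = +4 points. The extremes need complete overlap in one arm and none in the other.

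The preferred-term table in SAP 7.6.3 narrows this, because only subjects with an omitted term can add to the primary count. If one of the two select-AE subjects per arm had only bronchospasm, the combined count is 12 to 13 and the difference lies within ±1/50 = ±2 points.

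**5. Would a combined rate remove the dependence on recording?** Compare the two ways a site might record the same reaction:

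| Signs of the reaction | Recorded as | Primary as planned | Combined rate |
|---|---|---|---|
| At least one listed sign (e.g. rash) | Diagnosis only | Not counted | Counted |
| At least one listed sign | Symptoms | Counted | Counted |
| Unlisted signs only (e.g. chills) | Diagnosis only | Not counted | Counted |
| Unlisted signs only | Symptoms | Not counted | Not counted |

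The combined rate removes the dependence in the first pair. In the second pair it introduces a dependence that the planned endpoint does not have.

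**The case for a change.** The best case for a change is that this trial's value lies in a readable descriptive comparison, and how many subjects per arm had either kind of acute reaction is a basic question. A severe reaction coded only as *Infusion related reaction* stays outside the primary rate. Arm B has an observation step between infusions that Arm A lacks, so recording could differ by arm. The preferred-term tables do not show which subjects with an omitted term were already primary events, and the extra characterization in SAP 7.6.1 covers only events that meet the primary criteria. The remedy is one paragraph and one table from data already collected, and specifying it now would avoid choosing it after the results are known.

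The factual part stands: the two terms are absent, and the available text plans no combined count. The need for a change does not follow. Both terms have a named secondary endpoint with its own rate, difference and interval. SAP 7.6.9 adds AE summaries for Part 1, and the qualitative review in Protocol 8.1 can take in any individual severe reaction. Protocol section 6 asks for open-ended elicitation of adverse events without prompting for specific ones, which limits reporting bias, though it does not govern diagnosis-versus-symptom recording. The proposed rate would cure that dependence only in part, and it would not be directly comparable with the 24% benchmark.

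**Conclusion.** No change is needed. Using the SMQ as the primary list is a fair trade-off: it is a standard list with a prior rate to read against, and the sponsor's own reaction category sits beside it as a secondary endpoint analysed in the same way. Followed as written, the plan reports the omitted terms in full. A combined table would correct no number, rule or conclusion.

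The expected effect is small: about 1.6 of 50 subjects per arm at most, and under one point of half-width (17.4 - 16.7 = 0.7). Even the extreme ±4 points in the illustration is well inside an interval of ±16.7. These figures assume that the 3.2% from one earlier study carries over, although its terms and window are not given. The direction and size of any recording difference between arms are unknown.

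Two limits remain. The term match holds for MedDRA 19.0 and should be rechecked at the version used at database lock. The Core Safety SAP and the Data Presentation Plan, which the SAP cites, were not available, so a combined count may already be planned there. If the team wants a cross-tabulation of primary only, select AE only and both, it can be produced from the same data as an optional aid to reading.
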